## 9.5 Personal Data breaches

Personal data breaches will be immediately reported to the UCL Information Security Group (ISG) and the UCL Data Protection Officer [name] ([[contact]](mailto:[contact])), and to the Sponsor via the [UCL JRO research incident reporting form](#) (as per form and guidance: <https://www.ucl.ac.uk/legal-services/guidance/reporting-loss-personal-data>). The following information will be provided: full details as to the nature of the breach, an indication as to the volume of material involved, and the sensitivity of the breach (and any timeframes that apply). Sites will additionally follow their Trust incident reporting mechanisms and will document this within their Trial Master File and Investigator Site File.

The study has robust procedures in place to manage risks associated with participant disclosures of harm. If a participant discloses a serious risk of harm to themselves or others, the research team will follow an established distress protocol. Where possible, researchers will seek explicit consent before sharing concerns with a mental health professional. However, if a significant risk remains and the participant withdraws consent, confidentiality may need to be breached in line with safeguarding laws.

## 10. STATISTICAL CONSIDERATIONS

None in this study.

## 11. ASSESSMENT AND MANAGEMENT OF RISK

The table below summarise the risks and mitigations for testing the intervention above standard care that are being performed in a table:

Intervention	Potential risk	Risk Management
Interview of service user participants WP1	There may be a small possibility that the service user participant will get upset or emotionally distressed whilst taking part in the interviews and testing of intervention.	
What the study involves will be clearly explained to participants in the study information sheet and by researchers, and written informed consent will be received before participants join the study.
 
The interview topic guides will be developed with the study Lived Experience Advisory Panel (LEAP) that will consist of people with lived experience of MHA assessment.
 
If participants become distressed the study researcher will use their skills to make sure the participant feels as safe as possible. The lead researcher LB is an experienced mental health worker and has expertise in dealing with distress. The researchers will use guidance from sensitive subject research. This will include monitoring the participants' mental state, offering breaks, offering the opportunity to talk through their difficulties (if they want to), providing a safe and containing environment to conduct the research and ensuring a person-centred stance is taken. A distress protocol will be developed with the LEAP group to guide if a participant becomes upset.
 
A debriefing time will be offered after to discuss any emotions and questions raised in the interview and this time was viewed as valuable in a previous study.
 
Service user participants will be given a sheet with local and national support services for mental health (see Support Resources Sheet) for them to use after the interview if needed. We will also provide information on MHA assessments which the LEAP will develop.
 
For WP1, the participants will be asked to provide details of a support person- mental health worker, friend or family who they can talk to after if needed. Contact details will be requested at beginning of interview.
 
In the unlikely event that the participant becomes distressed, and it is not manageable by the researcher, will also contact their support person if there is concern that they are at a risk to themselves, or self-harming intent/suicide is disclosed. Each participant will be given a list of contacts if feeling any distress following the interview


		
or testing of intervention. This list has been devised with LEAP members. The researcher will follow the trusts safe visiting policy.
 
Within WP3, a member of their care team will be a participant as well and will be responsibility for any ongoing support needs.
 
Participants will be reminded that also free to withdraw at any point.
 
Participants who are deemed high risk by their clinical workers will be seen at the service where additional clinical staff are present.

Real world testing on clinical staff and service user participants		
If there is any distress or effect after the testing, then a harms log will be completed which will use information received from the service user or clinical team. This information will be discussed with supervisors and CI and advice sought about any requirement to modify the study procedures or the intervention, or pause the intervention phase of the study, in the event of concerns.

## 12. RECORDING AND REPORTING OF ADVERSE EVENTS

### 12.1 Definitions

Term	Definition
Adverse Event (AE)	Any untoward medical occurrence in a patient or trial participant, which does not necessarily have a causal relationship with the intervention involved.
Serious Adverse Event (SAE).	Any adverse event that: 
 
• results in death,
 
• is life-threatening*,
 
• requires hospitalisation or prolongation of existing hospitalisation**,
 
• results in persistent or significant disability or incapacity, or
 
• consists of a congenital anomaly or birth defect.
 
• Other ‘important medical events’ may also be considered serious if they jeopardise the participant or require an intervention to prevent one of the above consequences
 

\* A life-threatening event, this refers to an event in which the participant was at risk of death at the time of the event; it does not refer to an event which hypothetically might have caused death if it were more severe.

\*\* Hospitalisation is defined as an in-patient admission, regardless of length of stay. Hospitalisation for pre-existing conditions, including elective procedures do not constitute an SAE.

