### *5.1.5. Service user participants WP3 testing and refining*

Eligible participants will:

- (a) have experienced a Mental Health Act assessment within the last year
- (b) be able and willing to discuss this experience using the prototype intervention
- (c) be aged 18 and over and under 65
- (d) have capacity to consent at the time of recruitment.

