### **Recruitment of Service Users (WP1 and 3)**

#### **Methods of Recruitment:**

Service users will be recruited from acute inpatient wards, community mental health teams, and service user and carer groups. Recruitment strategies include:

- **Information Sharing via NHS Staff:** Staff will be informed about the study through Trust R&D departments, service managers, and Research Delivery Staff. Staff will identify and approach eligible service users, providing basic study information and recruitment materials (posters, flyers, participant information sheets).
- **Direct Self-Referral:** Service users who see study advertisements (e.g., posters, social media, advocacy networks) can contact the research team directly. When they contact, they will be asked permission to contact their care team to confirm suitability and capacity.
- **Targeted Databases:** In sites where service users have pre-agreed to be contacted about research, R&D staff will reach out to those who meet the inclusion criteria.
- **Use of Patient Record System:** Depending on the record system, it may be possible, to identify NHS staff working with eligible service users to target recruitment through using data analytics. This method was used in LB's previous research and does not involve any screening of personal identifiable data.
- **Community Engagement:** The research team will liaise with advocacy organisations and voluntary sector groups to promote the study.
- **Lived Experience Researchers involvement in recruitment:** Where appropriate, to increase recruitment LEAP members will be trained and paid to support recruitment by attending

community meetings on wards and other mental health settings. This approach been used successful in other studies and will be used if difficulties in recruitment.

- Diverse sample: To ensure that participants represent the population that are assessed/detained under the MHA, there might be targeted recruitment and adaptation of materials. For example, men and black people are overrepresented in detention figures.

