## **7.2 Discontinuation/withdrawal of participants**

In consenting to participate in the trial phase (WP3), participants are consenting to testing the and interview following. It is a one-off session.

It is always within the remit of the physician responsible for a service user to withdraw the service user from a trial (or certain aspects of the trial) for appropriate medical reasons, adverse events or new information gained about an intervention. A participant may be withdrawn from this WP whenever continued participation is no longer in the participant’s best interests, but the reasons for doing so must be recorded. Reasons for discontinuing may include deterioration in mental health.

The decision to withdraw a participant from treatment will be recorded in the CRF and medical notes/electronic health record system. If a participant explicitly states they do not wish to contribute further data to the trial their decision must be respected and recorded in the CRF and medical notes. Any inclusion of collected data needs to be used in accordance with GDPR and HRA guidance.

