## 12.2 Assessments of Adverse Events

WP1 and WP2 involve one-off interviews and stakeholder meetings, with no intervention. We do not propose to formally monitor SAEs in these phases of the study.

WP3 involves clinical staff using our novel intervention with six service user participants. It is possible in theory that service users could experience the intervention negatively and this could result in a serious adverse event. We will monitor SAEs in WP3 through feedback from the involved clinical and service user participants at the time of the intervention and in the follow-up interview.

In addition to SAE monitoring, we will also keep a Harms Log, recording any reported negative experiences of the interviews or intervention across all three Work packages. We will report the nature of the harm, which participant was affected, action taken to resolve the harm, and any actions planned to prevent recurrence. This harms log will be reviewed at least monthly by LB and her clinically qualified supervisors SJ and BLE, and by the wider project management group (see 15.2) at scheduled meetings. It will be available for review by the sponsor as requested. For this study, there will only be Adverse Events and Serious Adverse Events for work package 3.

Each adverse event (AEs) will be assessed for severity, causality, seriousness and expectedness as described below.

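### Read literally, the SAE footnote takes unplanned psychiatric readmission for the existing illness out of the hospitalisation criterion in WP3

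*Protocol*

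**What the plan says.** Section 12.1 lists the criteria that make an adverse event serious. One is that it "requires hospitalisation or prolongation of existing hospitalisation". A footnote to that criterion explains the term: "Hospitalisation is defined as an in-patient admission, regardless of length of stay". The footnote then carves out an exception: "Hospitalisation for pre-existing conditions, including elective procedures do not constitute an SAE". A further limb covers other important medical events, which "may also be considered serious if they jeopardise the participant" or call for action to prevent one of the listed outcomes.

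Section 12.2 confines formal SAE monitoring to WP3 and gives the reason: "It is possible in theory that service users could experience the intervention negatively and this could result in a serious adverse event". Section 7.2, on withdrawal from WP3, adds: "Reasons for discontinuing may include deterioration in mental health".

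On the population, the Study Summary describes the six WP3 service users as under mental health care. Section 5.1.5 requires each to "have experienced a Mental Health Act assessment within the last year". Section 5.3 gives the sources for WP1 and WP3: "Service users will be recruited from acute inpatient wards, community mental health teams, and service user and carer groups".

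Section 12.3 attaches two deadlines to SAE status: a completed form to the Sponsor within 5 working days of awareness and, where the event is unexpected and thought related, a report to the Health Research Authority within 15 days.

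**The concern.** An exclusion for pre-existing conditions does little harm where the condition is unrelated to the intervention. Here the intervention is a conversation about a coercive episode in the participant's own mental health care, and the pre-existing condition is the illness that led to that episode. If the session were badly received and an admission followed, the admission would most naturally be recorded as being for the existing illness. That is the class of admission that the footnote removes.

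At stake is whether such an admission is certain to be classified as an SAE, assessed for relatedness as one, and sent to the Sponsor and, where required, the Health Research Authority on time. If that is left to interpretation, three Trusts could classify the same event in different ways.

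**Working it through.** No arithmetic applies. Section 10 states that the study has no statistical considerations, and the question is what a definition includes. The check sets the sections side by side.

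1. **Starting rule (Section 12.1).** Any in-patient admission, of any length, makes an adverse event serious. Psychiatric admission is not treated separately, so without the exclusion it would count.

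2. **Scope of the exclusion (Section 12.1, footnote).** The excluded class is hospitalisation for pre-existing conditions. Elective procedures are introduced as something included in that class, so they do not limit it. The sentence has no condition about planning, timing or change in severity.

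3. **Anything that restores the excluded events (Sections 12.2 to 12.4).** Nothing does. The severity, causality, expectedness, recording and reporting sections neither bring back admission for relapse or worsening nor list psychiatric admission or detention as reportable.

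4. **Who is affected (Study Summary, Section 5.1.5).** Being under mental health care and assessed under the MHA in the past year implies an existing mental health condition in each of the six, although the eligibility criteria do not require a recorded diagnosis. On that assumption the exclusion can apply to any of them.

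5. **The prolongation limb (Section 12.1).** The criterion has two parts, admission and prolongation of a stay. The exclusion sentence names hospitalisation only. Recruitment from acute wards makes prolongation a live possibility, and the text can be read either way.

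6. **What turns on SAE status (Sections 12.2.3 and 12.3).** Section 12.2.3 says that no adverse events or SAEs are expected. An SAE judged related would therefore also be unexpected, and both the 5-working-day and the 15-day reports would be due. An admission that the footnote removes triggers neither on the strength of the admission alone.

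7. **What else could capture the event.**

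| Route | Section | What it gives | What it does not assure |
|---|---|---|---|
| Life-threatening or fatal event | 12.1 | Full SAE status | Does not cover an admission as such |
| Important medical events limb | 12.1 | SAE status at the assessor's discretion | Same classification across sites |
| Medical records and CRF | 12.2.4 | A record of every WP3 adverse event | An SAE deadline |
| Harms log | 11, 12.2 | At least monthly review by clinically qualified supervisors; power to seek changes or a pause | Sponsor sees it on request; no SAE deadline |
| Serious incidents and near misses | 12.7 | Prompt report to Sponsor and Trust, with no exclusion for pre-existing conditions | That a relapse admission is judged to qualify |

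8. **Against the stated purpose (Section 12.2).** SAE monitoring exists because the session might go badly enough to cause a serious event. A definition that sets aside admission for the participant's own illness works against that purpose.

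**The case against.** The best defence is that the footnote is standard wording meant for planned care of an unchanged condition, in a document logged as DRAFT 0.1 whose neighbouring sections still carry template prompts. That may well be the intention, but the sentence does not say so, and a site can only apply what is written.

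The defence is stronger on consequences, and three tempting inferences fail.

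- A reader might infer that WP3 would be blind to readmission. It would not: the routes tabulated above remain, and Section 11 makes a member of the participant's care team a fellow participant who is responsible for ongoing support.
- A reader might infer that no psychiatric admission could be an SAE. That goes too far. An admission after self-harm or an acute reaction to the session may be for a new event, life-threatening events count regardless, and the important medical events limb stays open.
- A reader might infer that prolonged stays are also excluded. The text does not settle this, and extending the exclusion to them would leave the prolongation limb with little content for psychiatric in-patients.

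It is also fair that the protocol does not rank harms. Section 7.2 gives deterioration only as a possible reason for discontinuing, and the risk table in Section 11 speaks of upset and distress. Calling readmission the main harm would be a reviewer's judgement. Nor does the small sample add to the case: any confidence limit for events among six people would be the same under any SAE definition.

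What stands is narrower. Unplanned readmission for the existing illness is not assured SAE status, and no other provision supplies the two deadlines for it with certainty.

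**Conclusion.** The concern holds as a defect of definition. On its literal wording the Section 12.1 footnote removes unplanned psychiatric readmission or detention for the existing illness from the hospitalisation criterion. It is in tension with the WP3 eligibility criteria and with the purpose of SAE monitoring in Section 12.2. Its reach is up to all six WP3 service users. Its effect is that the 5-working-day and 15-day reports are not assured; the event need not go unrecorded.

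This rests on two assumptions: that each WP3 service user has a mental health condition that predates the session, and that sites apply the footnote as written. The status of a prolonged psychiatric stay is unresolved rather than excluded.

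**What to change.** Reconcile the Section 12.1 footnote with Sections 5.1.5 and 12.2 in two steps.

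- Limit the exclusion to elective procedures and to admissions already planned before consent.
- State that in WP3 an unplanned psychiatric admission, an MHA detention, or prolongation of a current psychiatric stay after the session is an SAE, to be assessed for relatedness like any other.

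Naming prolongation removes the ambiguity in the present text. The change concerns classification and reporting only and leaves clinical care untouched.

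The cost is one footnote, a matching change to the SAE form, and possibly a few extra SAE forms among six participants. WP3 recruitment is planned from 7/27, so the change can be made before anyone is affected.

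The footnote alone will not guarantee capture. Section 12.2 gathers SAEs from feedback at the session and at the follow-up interview, and under Section 7.1.1 that interview may come straight after the session. A later admission could be missed under any definition, so the period over which SAEs are sought should be stated at the same time.

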## 12.2 Assessments of Adverse Events

WP1 and WP2 involve one-off interviews and stakeholder meetings, with no intervention. We do not propose to formally monitor SAEs in these phases of the study.

WP3 involves clinical staff using our novel intervention with six service user participants. It is possible in theory that service users could experience the intervention negatively and this could result in a serious adverse event. We will monitor SAEs in WP3 through feedback from the involved clinical and service user participants at the time of the intervention and in the follow-up interview.

In addition to SAE monitoring, we will also keep a Harms Log, recording any reported negative experiences of the interviews or intervention across all three Work packages. We will report the nature of the harm, which participant was affected, action taken to resolve the harm, and any actions planned to prevent recurrence. This harms log will be reviewed at least monthly by LB and her clinically qualified supervisors SJ and BLE, and by the wider project management group (see 15.2) at scheduled meetings. It will be available for review by the sponsor as requested. For this study, there will only be Adverse Events and Serious Adverse Events for work package 3.

Each adverse event (AEs) will be assessed for severity, causality, seriousness and expectedness as described below.

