### **Information on Case Report Forms**

The Case Report Forms (CRFs) will not bear the participant's name or other personal identifiable data. The forms will have the participant ID number. These CSF will include participant demographic and mental health diagnosis and MHA assessment or role details, work package, consent type, researcher observations from interviews, focus group or testing session, participant suggestion, any emotional responses, any adverse events and any post-session actions or support provided.

**Data custodian** is [name] (BLE).

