## 12.2.2 Causality

The assessment of relationship of adverse events to the intervention is a clinical decision based on all available information at the time of the completion of the case report form. The differentiated causality assessments will be captured in the trial specific AE Log and/or SAE form. The following categories will be used to define the causality of the adverse event:

Category	Definition
Related	A causal relationship between the intervention and an adverse event is at least a reasonable possibility, i.e., the relationship cannot be ruled out.
Not related	There is no reasonable possibility of a causal relationship between the intervention and an adverse event.
Not Assessable	Unable to assess on information available.

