#### 12.2.4 Recording of Adverse Events

All adverse events will be recorded in the medical records in the first instance.

All Adverse events will be recorded in the CRF following consent.

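### Section 12.2 confines AEs and SAEs to WP3, so a serious event attributed to a WP1 interview or WP2 workshop is logged as a harm but never assessed or reported as an SAE

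*Protocol*

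**What the plan says.** Section 12.2 explains that WP1 and WP2 consist of single interviews and stakeholder meetings without an intervention, and then says: "We do not propose to formally monitor SAEs in these phases of the study". In WP3, SAEs are picked up from staff and service users at the session and at the follow-up interview. A Harms Log runs across all three work packages. The lead researcher and two clinically qualified supervisors review it at least monthly, and the Project Management Group reviews it at its meetings. For the sponsor, "It will be available for review by the sponsor as requested". The same paragraph closes with the scope rule: "For this study, there will only be Adverse Events and Serious Adverse Events for work package 3".

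Other sections are worded without that limit:

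- Section 12.1 defines an adverse event as "Any untoward medical occurrence in a patient or trial participant", with no causal link required.
- Section 9.1 lists among the CRF contents "any emotional responses, any adverse events and any post-session actions or support provided". Section 9.2 shows that the CRF serves WP1, WP2 and WP3.
- Section 12.2.4 says: "All Adverse events will be recorded in the CRF following consent".
- Section 13.1 has the Project Management Group, which oversees the whole study, review adverse events that may be linked to the study.

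In Section 11, the row for WP1 service-user interviews gives distress as the potential risk. Its management text has the researcher contact the support person "if there is concern that they are at a risk to themselves, or self-harming intent/suicide is disclosed".

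**The concern.** The scope rule does more than decline to look for SAEs in WP1 and WP2. It says that none can exist there. A serious event that the team already knows about, and believes an interview caused, therefore cannot enter the assessment and reporting steps of Section 12. A researcher completing a WP1 CRF also meets an adverse-event item that Section 12.2 says cannot apply.

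At stake is a structured judgement on any such event: whether it is serious, whether the study caused it, whether it was expected, and whether it must go to the Health Research Authority. WP1 asks service users to recall an experience that the protocol itself describes as often distressing, and it enrols more of them than WP3.

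**Working it through.** The protocol has no statistical considerations, and the point rests on its text. The check is to set the passages side by side and follow one event through them.

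**Scope of adverse events**

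| Place in protocol | Limited to WP3? |
|---|---|
| 12.2, scope sentence | Yes |
| 12.1, AE definition | No |
| 9.1, CRF content | No |
| 9.2, CRF content list | No; names all three work packages, but is introduced as probable content |
| 12.2.4, AE recording | Not in its own words, but it is a subsection of 12.2 |
| 13.1, Project Management Group remit | No; the link is to the study, not to the intervention |

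The firm conflict is between the scope sentence and 12.1, 9.1, 9.2 and 13.1. Section 12.2.4 can be read either way.

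**Following one event.** Suppose a WP1 participant is admitted to hospital after an interview and the team thinks the interview contributed.

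1. *Seriousness.* Hospital admission is a seriousness criterion in 12.1. Under the scope sentence in 12.2 the event is nevertheless not an SAE.
2. *Assessment.* Section 12.2 requires each adverse event to be judged on four attributes, including causality and expectedness. As the event is not an adverse event under the scope sentence, none of these is judged.
3. *SAE form.* Section 12.3 sends SAE forms to the sponsor within 5 working days. This is not triggered.
4. *Expedited report.* Section 12.3 requires a report within 15 days for an event that is unexpected and related to the intervention. This is not triggered.
5. *What does happen.* The event is entered in the Harms Log with the action taken. If it meets the serious-incident description in 12.7, it goes to the sponsor and the Trust as soon as the team is aware of it.

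**Would deleting the scope sentence be enough?** No. The related category in 12.2.2 reads: "A causal relationship between the intervention and an adverse event is at least a reasonable possibility". WP1 and WP2 have no intervention, so an event caused by an interview still could not be classed as related and step 4 would still fail. Section 12.2.3 also frames expectedness around information on the intervention, and it says that no events are expected. For an SAE admitted to the process, relatedness is therefore the only practical gate to the 15-day report, and the wording of that gate decides the outcome.

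**Size.** Planned service users: WP1 up to 20 (Section 4.1), WP3 6 (Section 4.3).

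20 / (20 + 6) = 20 / 26 = 76.9%, about 77%.

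This counts people planned for WP1 and WP3. It leaves out lived-experience participants in WP2, for whom the protocol gives no separate number, and it says nothing about how often serious events would occur.

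**The case against.** The strongest reply is that the limit is deliberate and reasoned. WP1 and WP2 deliver no intervention, and both the causality categories and the 15-day trigger refer to the intervention, so the scope sentence fits them. Not searching for SAEs in one-off interviews is proportionate. This stands, and active monitoring need not be extended. It does not justify a rule that a known serious event possibly caused by the study cannot be an SAE.

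The other safeguards are real, and they rule out several stronger readings:

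- *A reader might infer that a WP1 harm has no route to the sponsor.* The documents do not support this. Section 12.7 is not limited to WP3, and its reporting is at least as prompt as the 5 working days in 12.3. Its heading carries an if-applicable qualifier, but its text is an instruction. Section 12.5 on urgent safety measures and the duty in Section 15 to tell the sponsor of monitoring concerns are not limited to WP3 either. What these routes lack is a relatedness and expectedness assessment and the 15-day report.
- *A reader might infer that a WP1 signal could be missed before WP3.* WP1 recruitment ends in 4/2026 and WP3 recruitment starts in 7/27. The Harms Log is reviewed at least monthly in between, so the signal would be known.
- *A reader might take self-harm or suicide as the named WP1 risk.* Section 11 names distress, as a small possibility. Self-harm disclosure is a contingency in the management text, and disclosure of intent is not by itself an SAE under 12.1.
- *A reader might say that the CRF is bound to hold forbidden entries.* A shared form may have items that do not apply to everyone, and the list in 9.2 is only probable content. The CRF shows inconsistent wording, not a certain error in the data.

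**Conclusion.** The point holds in a limited form. Section 12.2 contradicts the scope implied by 12.1, 9.1, 9.2 and 13.1. Read literally, it withholds SAE classification, relatedness and expectedness assessment and the 15-day report from a serious event attributed to a WP1 interview or WP2 workshop. Such an event would still be logged, reviewed and possibly sent to the sponsor as an incident.

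The gap applies to up to 20 of 26 planned WP1 and WP3 service users, and to WP2 participants as well. The number of affected events may well be zero, and the protocol gives no rate from which to estimate it. The conclusion assumes that the scope sentence is applied as written. Whether outside rules require expedited reporting for interviews cannot be judged from this document, and the point does not depend on it. The change is worth making because the affected text bears on participant safety and is cheap to correct.

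**What to change.** Keep active SAE monitoring confined to WP3, and make four text changes.

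1. In 12.2, replace the scope sentence with a rule such as:

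> SAEs are actively monitored in WP3 only. An event in WP1 or WP2 is recorded as an SAE, assessed under 12.2 and reported under 12.3 if it becomes known to the research team, meets a seriousness criterion in 12.1 and is possibly related to a study procedure (interview, focus group or workshop).

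2. In 12.2.2, 12.2.3 and 12.3, extend the reference from the intervention to the intervention or a study procedure. Without this, the first change would not open the 15-day route.
3. State that the Harms Log holds all other negative experiences in WP1 and WP2.
4. Align the CRF adverse-event item in 9.1 and 9.2, and the recording rule in 12.2.4, with this scope.

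The cost is a few sentences of protocol text and an occasional additional SAE form. The relatedness condition keeps out clearly unrelated hospital admissions, which matters because service users may be recruited from acute wards (Section 5.3). No new visits or staff are needed.
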